10.3.2 Subject Characteristics

Subject characteristics will be obtained at the Screening prior to randomization and will be summarized by treatment group and overall. Summaries will include descriptive statistics for

continuous measures (sample size, mean, standard deviation [SD], median, minimum, maximum) and for categorical measures (sample size, frequency and percentages).

Subject characteristics will be summarized on all study populations.

10.3.3 Treatment Compliance

Treatment compliance will be assessed in terms of the actual dose. Treatment compliance will be used to characterize the subjects and determine clinical evaluability for some analyses. Treatment compliance will be summarized within each treatment group by means of descriptive statistics (sample size, mean, SD, median, minimum and maximum).

10.4 Efficacy Analyses

A conclusion concerning efficacy will be based on evaluation of data in Part 2. A primary efficacy analysis will be conducted as well as a number of secondary efficacy analyses.

The primary efficacy endpoint (VIIS scaling severity as assessed by the Investigator in the target efficacy area) as well as all secondary efficacy variables that are captured on a continuous or semi-continuous scale (e.g., VIIS erythema score, central reader assessed VIIS scales, EQ-5D-5L, clinical global impression of severity, Patient/Observer impression scales, Patient-Reported Itching, CDLQI/DLQI, lipid biomarkers and TEWL) will be expressed as baseline to ending change scores. Two-sided 95% confidence intervals (CIs) will be computed and used descriptively for all variables but also to evaluate change relative to a standard for some variables (i.e., by determining whether the CI includes or excludes the standard).

The two-sided 95% CI for VIIS scaling severity will serve as the primary analysis and will be used to evaluate this primary endpoint as follows. An efficacy claim will be made if: 1) the lower confidence interval is above zero, 2) the mid-point of the confidence interval is at least 0.5 units is size, and 3) at least 50% of subjects have favorable change scores of one or greater.

The primary and secondary scores measured on a continuous or semi-continuous scale also will be evaluated using Mixed Model Repeated Measures to assess the effects of treatment (active vs. vehicle), time (per collection schedule), and treatment x time. In addition to descriptive statistics for the raw data used in each model, the LS means and standard errors will be reported for each main effect and interaction, as well as for treatment contrasts (i.e., active LS mean minus vehicle LS mean) at each data collection time point. If informative, covariates may be added to one or more models. Statistical significance unadjusted for multiplicity for main effects, interactions and contrasts will be reported. However, neither the main effect of treatment nor the treatment contrasts at time points are expected to be statistically significant ($p \le 0.05$) due to power restrictions at the between group level imposed by recruiting realities.

Response over time will be converted to one or more Area Under the Curve parameters and evaluated using a generalized linear model. VIIS outcome scores and other continuous or semicontinuous outcome variables will be evaluated using a Mixed Model Repeated Measures (MMRM) analysis. Conversion of VIIS or other scales to indicate response (yes/no) will occur (e.g., 0.5 VIIS improvement, 1 unit VIIS improvement) and will be evaluated as secondary endpoints. Logistic or Generalized Estimating Equation (GEE) modeling will be used to evaluate incidence of response overall and/or by time. Time to Event analysis (e.g., Kaplan-Meier with log rank test, proportional hazards [PH] modeling) will be used to evaluate time to response.

To increase statistical power, covariates may be incorporated into the computation of 95% confidence intervals (e.g., through the use of a mean centered covariate in a regression model to

predict the mean pre-treatment to post-treatment difference) and/or incorporated into logistic, GEE, PH, MMRM and generalized linear models.

Categorical variables other than responder status will be descriptively summarized in contingency tables. Selective inferential analysis at each time point or across time points will be conducted using non-parametric or exact statistics with or without further stratification as described in the SAP.

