1.2 Therapeutic Rationale for ADX-102 in Sjögren-Larsson Syndrome

1.3 Clinical Trials of ADX-102

1.3.1 Sjögren-Larsson Syndrome

Study NS-003 was a randomized, double-blind, vehicle-controlled, parallel group Phase 2 clinical trial evaluating the activity of ADX-102 1% topical dermal cream at a dose of 8 mg/cm² in subjects with ichthyosis associated with SLS.

A total of 12 male and female subjects aged 6 years or older (range 8 to 25 years) with genetically confirmed SLS and active ichthyosis on the lower extremities that was determined to be of moderate severity or higher were enrolled and randomized 1:1 to ADX-102 1% or vehicle. Subjects received study drug (ADX-102 1% or vehicle) once daily for 8 weeks.

The target area for treatment was an area on the lateral aspect of the lower leg, up to approximately 10 inches in height by 4 inches wide. In the cases where the lower leg did not have an ideal target area for treatment, the Investigator chose an area on another portion of the body as the target area. The lower leg was not utilized in only one subject whose right upper back was identified by the Investigator as the target treatment area.

In this Phase 2 clinical trial, the reduction in the severity of the ichthyosis in ADX-102-treated subjects was statistically significant relative to baseline. The most common reduction in the severity of the ichthyosis (assessed by the scaling ISS sub-score) in ADX-102-treated subjects over the duration of drug exposure (eight weeks) was one point from a median baseline severity of 3, representing an average change from moderate to mild disease. In addition, the activity of drug was statistically superior to that of vehicle. ADX-102-treated subjects showed greater mean and percentage decreases from baseline, and a higher proportion of ADX-102-treated subjects exhibited favorable individual responses than that of the vehicle-treated subjects for all the ISS sub-scores, except for excoriations.

ADX-102 1% w/w topical dermal formulation was generally well-tolerated and there were no significant or serious adverse events (SAE), or treatment-emergent adverse events (TEAEs) that led to treatment discontinuation.

pattern of changes was observed with ADX-102 for chemistry analytes, hematology parameters, or vital signs.

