Subjects will be consented and screened for eligibility. Qualified subjects will be randomized in a 2:1 ratio to either ADX-102 1% or vehicle. The appropriate sample size for Part 2 will be confirmed in Part 1. Subjects or caregivers will apply study drug (i.e., ADX-102 1% or vehicle) once daily to all affected areas of ichthyosis on the body (approximately 80 – 90% of BSA in a typical SLS patient).

The target efficacy area for all efficacy analyses at Week 24 will be one of the body sites as defined in the VIIS tool with Grade 2 or higher on the VIIS scaling severity as assessed by the Investigator.¹

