10.1 Sample Size

Part 1 of the study will assess the effect size on the VIIS scaling severity score with ADX-102 1% topical dermal cream, and will confirm the sample size needed for Part 2. Part 2 is expected to require approximately 30 subjects.

The approximate number of 30 subjects for Part 2 was based on the NS-003 Phase 2 study which used the ISS endpoint. The mean ISS Scaling sub-score change from baseline was -0.7 with a standard deviation of 0.52. Conservatively, the change was set to -0.5 and the standard deviation to 0.6. A sample size of 20 achieves 94% power to detect a difference of 0.5 between the null hypothesis mean of 0.0 and the alternative hypothesis mean of -0.5 with an estimated standard deviation of 0.6 and with a significance level (alpha) of 0.05 using a two-sided one-sample t-test. If the above assumptions remain, except that the standard deviation is increased to 0.7, then a sample size of 20 achieves a power of 85%. The sample size of 30 is therefore based on these estimates requiring 20 subjects to be treated with ADX-102 1%. As subjects will be randomized in a 2:1 ratio, 10 subjects will be treated with vehicle.

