These analyses will be carried out in an analogous fashion as for the primary efficacy variable (see above for a description of each analysis applied to the primary efficacy variable).

As with the primary efficacy variable (VIIS scaling), the within-group change from baseline will be the primary focus of interest in the MMRM analysis. Because SLS patient symptoms do not spontaneously improve over time, the within-group comparison provides a clinically meaningful evaluation. The planned analyses for selected secondary efficacy endpoint are outlined in Table 10.2.2.

Table 10.2.2: Analyses of the Secondary Efficacy Variables

	Analyses			
Secondary Efficacy Variable	MMRM	RESPONDER ANALYSIS (Estimating Equation)	AUC (Linear Model)	Survival
VIIS Erythema (Investigator Assessment)	✓		√	✓
VIIS Scaling (Photographic Assessment by Central Reader)	✓	✓	✓	✓
VIIS Erythema (Photographic Assessment by Central Reader)	✓		√	√

¹The 100 mm VAS will be analyzed using MMRM. Categorical outcomes will be displayed in a contingency table (Treatment x Category) containing frequency and percent occurrence of categorical outcomes.

²The total score (i.e., sum of 0 - 3 rating on 10 individual questions) will be analyzed using MMRM for change scores and a linear model for AUC. Responses to individual questions will be provided in a listing.

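### No condition of the Part 2 efficacy-claim rule uses the randomised vehicle arm, so improvement shared with vehicle counts as drug effect and a contrast favouring vehicle cannot stop a claim

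*Protocol*

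**What the plan says.** Protocol 3.1 sets up Part 2 as a controlled comparison: "Qualified subjects will be randomized in a 2:1 ratio to either ADX-102 1% or vehicle". Protocol 10.4, repeated in the synopsis, then gives the rule for an efficacy claim in three parts:

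- The opening part is a test against no change: "An efficacy claim will be made if: 1) the lower confidence interval is above zero".
- Next comes a minimum size for the estimate: "the mid-point of the confidence interval is at least 0.5 units is size".
- Last comes a responder threshold: "at least 50% of subjects have favorable change scores of one or greater".

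Section 10.4 does not name the arm to which the interval belongs, but the surrounding text supports a within-drug-arm reading. Section 10.1 sizes the trial on 20 ADX-102 subjects tested against a null mean of zero, "with a significance level (alpha) of 0.05 using a two-sided one-sample t-test". The go criterion for Part 2 in section 10 is the mean change on active treatment.

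Section 10.4 also plans a mixed model with active-minus-vehicle contrasts at each time point. These are reported, are not expected to reach significance because recruitment limits between-group power, and play no part in the rule.

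**The concern.** All three conditions measure change from baseline. That change contains the drug effect plus anything that happens in both arms, and the plan provides several routes to shared change:

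- a cream applied daily to all affected skin for 24 weeks;
- as-needed emollients allowed on treated skin (protocol 5.7.2.1);
- a target site chosen as the worst one, with a Grade 2 floor (protocol 5.6), which invites regression to the mean.

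Protocol 1.1 allows that moisturising creams do something, though it calls the results limited, variable and short-lived.

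The purpose of a randomised vehicle arm is to remove such shared change. Here the vehicle subjects can be tabulated but cannot alter the conclusion. A claim could be issued beside a randomised comparison showing no difference, or showing vehicle ahead.

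**Working it through.** **The plan's own figure.** Inputs from protocol 10.1: n = 20 on drug, mean change 0.5, SD 0.6 or 0.7, two-sided alpha 0.05. Power = P(|T| > 2.093), where T is noncentral t with 19 df and noncentrality 0.5·√20/SD.

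- SD 0.6: noncentrality 3.73, power 94.2%. This matches "A sample size of 20 achieves 94% power to detect a difference of 0.5".
- SD 0.7: noncentrality 3.19, power 85.8%. The plan says 85%.

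**The same inputs between arms.** With 20 v 10 and vehicle change zero, noncentrality is 0.5/(SD·√(1/20 + 1/10)) on 28 df.

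- SD 0.6: 2.15, power 54.7%.
- SD 0.7: 1.84, power 42.9%.

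The protocol is therefore right that between-group significance would be hard to reach.

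**Claim rate when drug equals vehicle.** The documents give no vehicle mean, so the shared improvement m is an assumption and is shown over a range. The VIIS is scored in whole grades 0 to 4 (SAP 10.1). Assumed improvements are −1, 0, 1 or 2, with 5% at −1, 5% at 2, m − 0.05 at 1 and the rest at 0 (for m = 0: 5%, 90%, 5%, 0%). For m above 0 the variance is 0.20 + m − m², so the SD is 0.67 at m = 0.5 and 0.64 at m = 0.7. Each scenario used 200,000 simulated trials of 20 drug and 10 vehicle subjects, applying the three conditions to the drug arm. The last column adds the requirement that the drug mean improvement exceed the vehicle mean.

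| Shared improvement (grades) | Rule as written | With direction check |
|---|---|---|
| 0 to 0.1 | about 0% | about 0% |
| 0.2 | 0.2% | about 0.2% |
| 0.3 | 4% | about 4% |
| 0.4 | 21% | 16% |
| 0.5 | 51% | 33% |
| 0.6 | 79% | 42% |
| 0.7 | 94% | 45% |

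Simulation error and the handling of tied means move the last column by less than one point. At a shared 0.7, about 41% of all trials earn the claim with the vehicle mean strictly better. If the drug truly gives 0.6 and vehicle 0.8, the rule still grants the claim in about 79% of trials.

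**A check by hand.** If scores are only 0 or 1, conditions 2 and 3 both reduce to at least 10 of 20 improving, and condition 1 then follows (10 of 20 gives a lower limit of 0.5 − 2.093·0.513/√20 = 0.26). The claim rate is P(Bin(20, p) ≥ 10): 4.8% at p = 0.3, 24.5% at 0.4, 58.8% at 0.5, 87.2% at 0.6 and 98.3% at 0.7.

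**Sensitivity to shape.** Normal changes (SD 0.6) rounded to whole grades give 0.1% at 0, 5% at 0.25, 10% at 0.3, 27% at 0.4, 51% at 0.5, 75% at 0.6 and 91% at 0.7. Scores of 0, 1 or 2 with mean 0.5 and SD 0.6 give 39%. Unrounded normal scores give only 0.3% at 0.5 and 6% at 0.7, because condition 3 then rarely passes; whole-grade scoring makes that model less relevant.

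**Cost of the check when the drug works** (drug mean 0.7, claim rate about 94% without it): no loss with vehicle at 0, then 93.7% to 93.2% at 0.1, 93.7% to 91.9% at 0.2 and 93.7% to 88.9% at 0.3.

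**The case against.** The protocol gives its reason beside the rule: recruitment in this disease does not allow adequate between-group power. The 55% and 43% above bear that out. The contrasts are still reported at every time point, so an adverse comparison would be visible, and conditions 2 and 3 ask for more than significance. All of this stands. It explains why significance against vehicle is not required; it does not explain why the direction of the comparison is left out.

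The Phase 2 evidence also favours the sponsor. Protocol 1.3.1 says drug activity in NS-003 was statistically superior to vehicle. As an illustration, assume a two-sample t-test with 6 per arm, SD 0.52 in both arms, and that the 0.7 change in section 10.1 is the drug mean. Significance then needs a difference of 2.228·0.52·√(2/6) = 0.67, which puts vehicle near zero. The test and endpoint behind the superiority statement are not given, so this is not proof, but it points away from a large vehicle response.

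A reader might infer from "ADX-102-treated subjects showed greater mean and percentage decreases from baseline" that vehicle also improved. The phrase is equally compatible with no change on vehicle.

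A reader might also take "Because SLS patient symptoms do not spontaneously improve over time, the within-group comparison provides a clinically meaningful evaluation" (SAP 10.2) as the justification for the Part 2 rule. The SAP limits itself to Part 1, and that sentence concerns its own within-group analysis. Even if carried over, it speaks to natural history and not to the effect of a daily cream or of site selection.

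**Conclusion.** The structural point holds on the text and needs no numerical assumption: no claim condition uses the vehicle arm, and the planned contrast cannot block a claim. It does rest on reading the interval as within the drug arm, which 10.4 does not say outright but sections 10 and 10.1 support.

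The size is conditional. Claim rates for a drug no better than vehicle stay below 5% in the main model up to a shared improvement of 0.3 grade, and rise from 21% at 0.4 to 94% at 0.7. A reader might infer that an ineffective drug would generally earn the claim in half to nine in ten trials. The documents do not support that: it requires vehicle alone to improve by about 0.5 to 0.7 grade, which equals the planning effect and the Phase 2 change in section 10.1, and no vehicle figure is given. Nor do the documents show that the vehicle response is small under 24 weeks of near whole-body application, and the rule has no safeguard if it is not. This should be fixed as a cheap improvement; it is not a fatal flaw.

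**What to change.** In protocol 10.4, the synopsis and the SAP text for Part 2:

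- Add condition 4: the Week 24 active-minus-vehicle contrast in VIIS scaling change, from the mixed model already planned, favours ADX-102 on its point estimate; significance is not required. State the direction in words, because section 10.1 and the SAP code improvement as negative while condition 1 treats it as positive.
- If conditions 1 to 3 hold and condition 4 does not, report improvement from baseline not distinguished from vehicle, and make no efficacy claim.
- Report the contrast and its 95% CI beside the primary result.

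This needs no new patients, data or model, and leaves the within-arm primary analysis and sample size unchanged. With a drug mean of 0.7, it costs about 0 to 2 points of claim probability if vehicle improves by 0 to 0.2 grade, and about 5 points at 0.3.

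It is a direction check only. False claims fall to about 16%, 33%, 42% and 45% at shared improvements of 0.4, 0.5, 0.6 and 0.7, so a met claim should still be described as change from baseline, with the between-arm estimate and CI alongside. Requiring the between-arm 95% CI to exclude zero would hold false claims near 2.6 to 2.8% (0/1 scores). At a true difference of 0.5, however, 90% power would need about 69 subjects (SD 0.6) or 93 (SD 0.7), which the protocol's recruitment argument rules out.

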	Screening ¹	Baseline Visit 1 ¹	Visit 2	Visit 3	Visit 4	Visit 5	Visit 6	Visit 7	ET Visit 8 ²	Safety Follow-up Visit 9
	Day -7 to -1	Week 1 Day 1	Week 1 Day 2	Week 4 ± 3 days	Week 8 ± 5 days	Week 12 ± 3 days	Week 16 ± 5 days	Week 20 ± 3 days	Week 24 ± 5 days	Week 28 ± 5 days
Evaluation	Site Visit	Site Visit	Site Visit	Telephone	Site Visit	Telephone	Site Visit	Telephone	Site Visit	Site Visit
Informed consent / assent	Х									
Eligibility review	Х	Х								
Demographics / medical history	Х									
Concomitant medications	Х	Х	Х	Х	Х	Х	Х	Х	Х	X
Adverse events	Х	Х	Х	Х	х	х	х	х	Х	x
Urinalysis / pregnancy test ³	Х	Х			Х		Х		Х	
12-Lead ECG (see Table 1-1)	Х	Х			Х				Х	
Holter Monitoring		Х			Х				Х	
Vital Signs (see Table 1-1)	х	Х	Х		Х		Х		х	
Physical exam ⁴	Х	Х	Х		Х		х		Х	
Dermatologic exam	х	Х	Х		Х		Х		х	Х
Digital photography⁵		Х			Х		х		Х	Х
VIIS (Investigator-assessed)		X ⁶	Х		х		х		Х	Х
Global impression of severity		Х			Х		х		Х	Х
Patient/Observer-reported scales ⁷		Х			Х		Х		х	х
PD sample collection ⁸		Х	Х		Х		Х		х	
Clinical laboratory testing ⁹	х	Х			Х		Х		х	
PK sample collection ¹⁰ (see Table 1-1)		Х	Х		Х		Х		Х	
Randomization		Х								
Administer study drug ¹¹		Х	Х	Х	Х	Х	Х	Х		
Dispense study drug & diary			Х		Х		Х			
Collect study drug & diary					Х		Х		Х	
Exit interview									X ¹²	

ECG = electrocardiogram; ET = early termination; PD = pharmacodynamic; PK = pharmacokinetic; VIIS = Visual Index for Ichthyosis Severity

1. Samples collected for urinalysis and clinical laboratory tests may be analyzed at a local lab.

- 2. Subjects who terminate early from the study will undergo, if possible, all of the assessments and procedures scheduled for Visit 8 (Week 24).
- 3. Urine pregnancy test for female subjects of child-bearing potential only. Tests can be analyzed at the study site.
- 4. Complete physical exam, including height and weight collection, performed at Screening Visit only; symptom directed physical exams at all other timepoints.
- 5. Subjects should refrain from bathing and applying study drug or as-needed topical symptom control therapy (emollients) to the treatment area within 12 hours of obtaining digital photographs.
- 6. VIIS must be independently assessed by two different Investigators at Baseline Visit 1 only.

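### Part 2 leaves baseline VIIS an optional, unnamed covariate in the drug-versus-vehicle MMRM, and lets covariates narrow the one-group primary 95% CI without any real gain in precision

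*Protocol*

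**What the plan says.** Protocol 10.4 makes the two-sided 95% CI for change in VIIS scaling the primary analysis. A claim needs three things: a lower limit above zero, a midpoint of at least 0.5, and at least half of subjects improving by one unit or more. The section does not name the group. Section 10.1 sizes the trial on the 20 active subjects "with a significance level (alpha) of 0.05 using a two-sided one-sample t-test", so I read the CI as a one-group interval in the active arm.

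The randomised comparison is a further analysis, described as "Mixed Model Repeated Measures to assess the effects of treatment (active vs. vehicle), time (per collection schedule), and treatment x time". On covariates for it, the section says "If informative, covariates may be added to one or more models". It also says that between-group significance is not expected, because recruitment limits power.

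A later paragraph of 10.4, repeated in the synopsis, says "To increase statistical power, covariates may be incorporated into the computation of 95% confidence intervals". Its example is a mean-centred covariate in a regression for the mean pre-to-post difference. The same sentence extends the option to the MMRM and the other models.

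Baseline VIIS is scheduled for all Part 2 subjects. Table 2, footnote 6, adds that "VIIS must be independently assessed by two different Investigators at Baseline Visit 1 only".

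The protocol promises a SAP for both parts, but SAP section 2 limits the SAP to Part 1. Its primary MMRM (10.1) uses drug-treated subjects only and includes baseline on condition that it proves useful. SAP 8.2 adds covariates to a model where they materially raise power.

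**The concern.** There are two separate issues.

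1. **The randomised contrast.** With 20 and 10 subjects, chance baseline imbalance and between-subject variance cost a good deal, and baseline adjustment recovers part of that cost from data already collected. As written, nobody can tell beforehand whether baseline will be in the model, and an undefined test of usefulness invites a choice made after seeing the results. This contrast is the only VIIS analysis that separates drug effect from vehicle response and from drift in scoring.

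2. **The one-group interval.** In a single arm there is no imbalance to correct. Centring a covariate at the sample mean cannot improve the estimate of the population mean change. It only removes from the standard error a source of variation that is really there. An interval reported as 95% would then cover less often than that.

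**Working it through.** **Inputs.** From Protocol 10.1: 20 active and 10 vehicle, two-sided alpha 0.05, within-group change 0.5, SD of change 0.6 or 0.7 (taken from the Phase 2 ISS, not VIIS). Assumed, because the documents give no figure: a between-group difference of 0.5, which means no vehicle change, with 0.3 as an alternative; and a change-baseline correlation ρ of 0.3, 0.5 or 0.7.

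**The plan's own figures.** One-sample noncentral t, 19 df, noncentrality (0.5/SD) × √20. SD 0.6 gives 94.2% and SD 0.7 gives 85.8%. The protocol states 94% and 85%, so both reproduce.

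**Drug versus vehicle.**
- Unadjusted: noncentrality = difference / (SD × √(1/20 + 1/10)), 28 df. For 0.5 and SD 0.6: 0.5 / (0.6 × 0.3873) = 2.152, power 54.7%.
- Baseline-adjusted: replace SD by SD × √(1 − ρ²), 27 df. At ρ = 0.5: 0.6 × 0.866 = 0.520, noncentrality 2.485, power 66.8%.

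| Difference | SD | No baseline | ρ = 0.3 | ρ = 0.5 | ρ = 0.7 |
|---|---|---|---|---|---|
| 0.5 | 0.6 | 54.7% | 58.5% | 66.8% | 82.7% |
| 0.5 | 0.7 | 42.9% | 46.2% | 53.7% | 70.2% |
| 0.3 | 0.6 | 23.9% | 25.7% | 30.1% | 41.4% |
| 0.3 | 0.7 | 18.8% | 20.1% | 23.4% | 32.1% |

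At a difference of 0.5 the gain is 12.2 and 10.8 points at ρ = 0.5, about 3 to 4 points at 0.3, and about 27 to 28 at 0.7. At a difference of 0.3 and ρ = 0.5 it is 6.3 and 4.7 points.

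The closed form ignores the price of chance baseline imbalance. Simulated ANCOVA at a difference of 0.5 and ρ = 0.5 (100,000 trials) gives about 65% at SD 0.6 and 52.3-52.6% at SD 0.7, gains of roughly 10.5 and 9.5 points.

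Here ρ is the correlation of change with baseline. If one thinks instead of baseline with follow-up, at equal variances, the residual fraction is (1 + r)/2. The two agree at 0.5 (both 0.75), but the gain then falls as r rises.

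**One-group interval, n = 20.**
- The fitted intercept is the mean change minus slope × the mean of the centred covariate. That last mean is zero, so the intercept equals the raw mean change.
- The true variance of the mean change is σ²/n. The regression reports about σ²(1 − ρ²)/n. The missing ρ²σ²/n is the sampling variation of the baseline mean.
- Width factor √(1 − ρ²): 0.95, 0.87, 0.71 at ρ = 0.3, 0.5, 0.7. Simulated: 0.96, 0.87, 0.72.
- Simulated two-sided error under zero change: about 6%, 8.5% and 15%, against 5% unadjusted. In the direction of improvement: about 3.0%, 4.3% and 7.5%, against 2.5%.

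**Effect on the claim rule.**
- With a midpoint of at least 0.5, the unadjusted lower limit exceeds zero whenever 0.5 − 2.093 × SD/√20 > 0, that is for SD below 0.5 × 4.472/2.093 = 1.07. At SD 0.6 to 0.7 the midpoint condition binds.
- Under zero true change, a midpoint of 0.5 lies 0.5/(0.6/√20) = 3.73 standard errors out at SD 0.6 and 3.19 at SD 0.7. Simulated chances of passing the first two conditions are about 0.01% and 0.07%, the same with and without the covariate.
- At a true change of 0.5, the decision differed in at most 0.005% of simulated trials.

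**The case against.** - **The protocol does not exclude baseline.** A reader might infer that baseline is left out of the MMRM while covariates are kept for the CI. The text does not support that: 10.4 permits covariates in the MMRM twice, once in the very sentence that offers them for the CI. This objection stands. The defect is that the term is optional, unnamed and conditional.
- **Detail was deferred to a SAP.** True, but the SAP supplied covers Part 1 only, and its own covariate rules are conditional in the same way.
- **The power gain rests on assumptions.** This stands. The correlation and the between-group difference are not in the documents, and any vehicle improvement shrinks both power and gain. The calculation is a single-visit ANCOVA on normal data, whereas VIIS is a 0-4 score with baseline restricted to grades 2 to 4.
- **The MMRM does not decide the claim.** Correct. Even with the gain, power is only about 52% to 67% under the central assumptions.
- **The narrowed interval is valid for another target.** For the mean change at the sample's own mean baseline, simulated coverage stays at 95.0%. But a claim about a treatment concerns the population, and 10.1 sizes the trial on the ordinary one-sample test.

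**Conclusion.** Both points hold, with limited reach.

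Pre-specifying baseline VIIS would add about 10 to 12 points of power to the Part 2 randomised contrast if the true difference is 0.5 and the change-baseline correlation is 0.5. The gain is small at a correlation of 0.3 and large at 0.7. The case for fixing the term does not depend on the exact figure: the data are collected, the cost is negligible, and a choice made after seeing the results is avoided.

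The covariate option for the one-group CI does not produce a valid 95% interval for the population mean change. A reader might go further and infer that it inflates false efficacy claims. The documents do not support that, because the 0.5 midpoint rule settles the matter at SD 0.6 to 0.7. What suffers is the reported precision of the primary result. The option also covers intervals for other variables that 10.4 compares with a standard, where no midpoint rule is stated to limit the effect.

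**What to change.** In Protocol 10.4, and in a SAP that covers Part 2:

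1. State that the Part 2 active-versus-vehicle MMRM of change in VIIS scaling will include baseline VIIS scaling in the target efficacy area, and its interaction with time, as fixed covariates. Say which of the two baseline Investigators' scores is used. Do the same for the other continuous scales that have a baseline.
2. Replace the conditional covariate wording with a named list fixed before unblinding.
3. Delete the covariate option and the mean-centred example from the one-group 95% CI, in 10.4 and in the synopsis, so that the primary interval is the unadjusted one-sample interval on which 10.1 is sized.

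Cost: wording, a few degrees of freedom in the MMRM, and a primary CI somewhat wider than the covariate version would have shown. No new data or subjects are needed.
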